6.1.1. Patient Populations for Analysis

Patient populations are defined in [Table AMAJ.6.1](#) along with the analysis they will be used to conduct. Patients will be analyzed according to the treatment to which they were assigned for all populations. [Table AMAJ.6.2](#) describes the treatment groups and the comparisons for each study period and the analysis population.

Table AMAJ.6.1. Patient Populations for Analysis

Population	Description
All Entered Patients	All patients who signed informed consent.
Intent-to-Treat (ITT) Population	All randomized patients, even if the patient does not take the assigned treatment, does not receive the correct treatment, or otherwise does not follow the protocol. Unless otherwise noted, efficacy and health outcomes analyses for the both induction period and combined induction/maintenance periods will be conducted on this population.
Induction Safety	All randomized patients who received at least 1 dose of study treatment . Safety analyses for the induction period will be conducted on this population.
All Active Treatment Safety	All randomized patients who received at least 1 dose of mirikizumab or secukinumab .
Induction PPS	All randomized patients who do not have important protocol deviations excluded from per protocol analysis (IPDPP) in the induction period. IPDPP are described in a separate document referred to as the “The AMAJ Trial Issues Management Plan”. These patients will be used to reanalyze the primary endpoints only.
Induction and Maintenance PPS	All randomized patients who do not have IPDPP in the combined induction/maintenance periods. IPDPP are described in a separate document referred to as the “The AMAJ Trial Issues Management Plan.” These patients will be used to reanalyze the selected major secondary endpoints of PASI 90 and sPGA (0,1) at Week 52.

Abbreviations: PASI = Psoriasis Area and Severity Index; PASI 90 = $\geq 90\%$ improvement in PASI from baseline; PPS = per protocol set; sPGA = static Physician’s Global Assessment.

Table AMAJ.6.2. Treatment Groups and Comparisons for Each Study Period and Analysis Population

Study Period	Analysis Population	Treatment Groups	Inferential Comparisons
Induction Period	ITT; Induction Safety; Induction PPS	placebo Q4W; 300 secu; 250 miri Q4W	300 secu vs placebo Q4W; 250 miri Q4W vs placebo Q4W; 250 miri Q4W vs 300 secu

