6.1.1.1. Study Time Intervals

[Table AMAJ.6.3](#) displays a list of study periods along with the definition of which patients will be considered to have entered the study period and when the individuals start and end the study period. The table shows both a date and a time.

To calculate the length of any time interval or time period in this study the following formula will be used:

$$\text{Length of interval (days)} = \text{End Date} - \text{Interval Start Date} + 1$$

Only for the purpose of calculating the length of study period time intervals, the words “prior to” in [Table AMAJ.6.3](#) should be understood to mean “the day before” while the words “after” should be understood to mean “the day after.”

To convert any time length from days to years, the following formula will be used:

$$\text{Length of interval (years)} = \text{Length of interval (days)} / 365.25$$

To convert any time length from days to weeks, the following formula will be used:

$$\text{Length of interval (weeks)} = \text{Length of interval (days)} / 7$$

Table AMAJ.6.3. Definition of Study Period Time Intervals

Study Period	Start Definition	End Definition
Screening: All patients who sign informed consent are considered as entering the Screening Period.	Informed consent date	Prior to the start of induction
Induction Period: All patients who are randomized to the study are considered as entering the Induction Period.	At the first injection following randomization date/time ^a . For patients who are randomized but not dosed, the Induction Period starts on the date of randomization.	Prior to the start of maintenance. For patients who discontinue before or on the Week 16 visit, the induction period ends at the last date of treatment discontinued date or last treatment visit date.
Maintenance Period: All patients who had any Week 16 to Week 52 visits (except the ones who discontinued the study at Week 16) are considered to have entered the Maintenance Period.	At the Week 16 dosing date/time. ^a If a patient is unable to be dosed at the Week 16 visit, the Maintenance Period starts at the Week 16 visit. If the patient misses the Week 16 visit, the Maintenance Period starts at Day 118.	After the Week 52 visit date. If patients discontinued prior to Week 52, the Maintenance Period ends at the last date of treatment discontinued or last treatment visit date.

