Induction and Maintenance Periods	Use the definition of the start of the Induction Period.	Use the definition of the end of Maintenance Period.
Follow-up Period: All patients who had Visit 801 or 802 are considered to have entered the Follow-up Period.	The latest of the following dates: (1) after the end of the Induction Period as described above, (2) after the end of the Maintenance Period as described above	The last date of the last study visit and study disposition date
All Active Treatment Periods: All patients who are treated with mirikizumab or secukinumab are considered to have entered this period.	For mirikizumab and secukinumab induction treatment groups, use the definition of the start of Induction Period; For placebo/250 miri treatment group, use the definition of the start of Maintenance Period.	The latest of the following dates: (1) the end of the Induction Period, (2) the end of the Maintenance Period
All Periods (Induction + Maintenance + Follow-up Periods)	Induction period start date	The last date of the last study visit and study disposition date

^a Missing dose time will be imputed as the earliest time that is consistent with available data about dose time. For example, suppose the minutes are missing but hour is present; in this case, we would impute the minutes to be 0.

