6.14.1. Extent of Exposure

Duration of exposure to study treatment will be summarized by treatment group for each of the 2 safety analysis populations (that is, Induction Safety and All Active Treatment Safety). For the treatment period of interest associated with each safety analysis population, exposure will be calculated as the time period length in years (see Section 6.1.1.1) with start and end dates described in Table AMAJ.6.3. The following periods will be used for calculations:

- For the Induction Safety Population, the Induction Period Interval will be used.
- For the All Active Treatment Safety Population, 1) for patients randomized to mirikizumab and secukinumab, the Induction and Maintenance Period Interval will be used; 2) for patients randomized to placebo and entering the Maintenance Period, the Maintenance Period Interval will be used.

Total patient-years (PY) of exposure will be reported for both safety analysis populations by treatment group (see Table AMAJ.6.2). Descriptive statistics will be provided for patient-weeks of exposure and the frequency of patients falling into different exposure ranges will be summarized:

- >0, ≥4 weeks, ≥8 weeks, ≥12 weeks, ≥16 weeks, ≥ 24 weeks, ≥32 weeks, ≥40 weeks, ≥48 weeks
- >0 to <4 weeks, ≥4 weeks to <8 weeks, ≥8 weeks to <12 weeks, ≥12 weeks to <16 weeks, ..., ≥48 weeks

Additional exposure ranges may be considered if necessary. No p-values will be reported in these tables as they are intended to describe the study populations, rather than test hypotheses about them.

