6.14.2. Adverse Events

A treatment-emergent adverse event (TEAE) is defined as an event that first occurred or worsened in severity after baseline. The MedDRA Lowest Level Term (LLT) will be used in the treatment-emergent computation. The maximum severity for each LLT during the baseline period will be used as baseline. The treatment period will be included as postbaseline for the analysis. For events with a missing severity during the baseline period, it will be treated as ‘mild’ in severity for determining treatment-emergence. Events with a missing severity during the postbaseline period will be treated as ‘severe’ and treatment-emergence will be determined by comparing to baseline severity. For events occurring on the day of first taking study medication, the start times of the study treatment and AE will be used to determine whether the event was pre- versus posttreatment. If start time for the AE is missing, it will be assumed to have started in the later period.

Summary tables as described in [Table AMAJ.6.7](#) will be presented for the 2 safety populations/periods as indicated. Summary tables will include the number and percentage of patients reporting an event. For events that are gender-specific (as defined by MedDRA), the number of participants at risk will include only patients from the given gender. Comparisons will be performed using Fisher’s exact test. For document writing purposes, tests with 2-sided p-values less than 0.05 will be referred to as “having strong evidence for a treatment difference”, unless otherwise noted. However, p-values should not be over interpreted for these safety analyses. Except for prespecified hypotheses, they correspond to data-driven hypotheses and hence are only useful as a flagging mechanism.

For the 2 safety populations, the baseline period and postbaseline will be defined as follows:

- *Induction Safety Population*: The baseline period is the Screening Period. The postbaseline period will be the Induction Period.
- *All Active Treatment Safety Population*: The baseline period for patients randomized to mirikizumab and secukinumab during induction is the Screening Period. For patients randomized to placebo, the baseline events are those events which are ongoing at the time of the first injection with mirikizumab (that is, the baseline period is a moment in time). Two different postbaseline periods will be used:
 - For “all miri” and “all secu”, the All Active Treatment Periods will be used.

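### For placebo patients first given mirikizumab after Week 16, the All Active Treatment Period can start before the first mirikizumab injection that the SAP uses as their safety baseline

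*SAP*

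**What the plan says.** Three sets of rules in the SAP meet here.

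- **Start of the period (6.1.1.1, Table AMAJ.6.3).** For the All Active Treatment Periods: "For placebo/250 miri treatment group, use the definition of the start of Maintenance Period". Maintenance normally starts at the Week 16 dose, but there are two fallbacks: "If a patient is unable to be dosed at the Week 16 visit, the Maintenance Period starts at the Week 16 visit", and "If the patient misses the Week 16 visit, the Maintenance Period starts at Day 118". Neither needs a mirikizumab dose.
- **Who is included.** The All Active Treatment Safety population is randomized patients "who received at least 1 dose of mirikizumab or secukinumab" (Table AMAJ.6.1). Table AMAJ.6.3 applies the same condition to the period: "All patients who are treated with mirikizumab or secukinumab are considered to have entered this period". A placebo patient who misses the Week 16 dose but is dosed later therefore qualifies.
- **Baseline and exposure.** In 6.14.2, for patients randomized to placebo, "the baseline events are those events which are ongoing at the time of the first injection with mirikizumab"; the section calls this a moment in time. It then makes the All Active Treatment Periods the postbaseline period for the all-miri column. Section 6.14.3 likewise takes the last laboratory value before the first mirikizumab treatment as baseline, and uses the postbaseline periods of 6.14.2. For exposure, 6.14.1 says that "for patients randomized to placebo and entering the Maintenance Period, the Maintenance Period Interval will be used".

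**The concern.** For a patient dosed at Week 16, period start and safety baseline coincide. For a patient first dosed later they do not: the postbaseline period opens before the baseline moment. Time before any mirikizumab is then labelled as mirikizumab time, and what happens in it may be reported under mirikizumab.

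The patient-years are few, but rare safety outcomes are single counts. One misplaced serious event or transaminase elevation can be visible in a column even when the exposure total barely moves. The gap may also not be a random slice of time, since a dose may be missed for a safety reason. That last point is inference; the documents do not give reasons for missed Week 16 doses.

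**Working it through.** **1. The plan's own figure.** Week 16 falls on Day 16 × 7 + 1 = 113. The visit tolerance is ±5 days (Schedule of Activities, Protocol addendum section 4.1). The end of the window is 113 + 5 = Day 118, which reproduces the fallback in Table AMAJ.6.3.

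**2. Length of the gap.** After Week 16, the next scheduled mirikizumab dose for the placebo arm is Week 20 (SAP 5.1.3), Day 141 ± 5, so Days 136 to 146. Gap = day of first mirikizumab dose − day on which the period starts.

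| Situation at Week 16 | Nominal | Shortest | Longest |
|---|---|---|---|
| Visit attended, not dosed | 141 − 113 = 28 days | 136 − 118 = 18 | 146 − 108 = 38 |
| Visit missed (start Day 118) | 141 − 118 = 23 days | 136 − 118 = 18 | 146 − 118 = 28 |

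These figures assume that the first mirikizumab dose is given at the Week 20 visit. An earlier unscheduled dose would shorten the gap; missing Week 20 as well would lengthen it.

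**3. Share of one patient's exposure.** The Week 52 visit is Day 365. Table AMAJ.6.3 ends Maintenance after that visit, which 6.1.1.1 reads as the day after, Day 366. From Day 113 the interval is 366 − 113 + 1 = 254 days, so a 28-day gap is 28/254 = 11% of it. From Day 118 it is 366 − 118 + 1 = 249 days, and 23/249 = 9%.

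**4. Share of the columns.** SAP 5.2 plans 111 placebo and 888 mirikizumab patients. If all complete Week 52:

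- placebo/250 miri: 111 × 254/365.25 = 77.2 patient-years
- patients randomized to mirikizumab: 888 × 366/365.25 = 889.8 patient-years
- all miri: 77.2 + 889.8 = 967.0 patient-years

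The documents do not say how many placebo patients go undosed at Week 16 and are dosed later, so 1% to 10% is an assumption. Patient-years before mirikizumab = 111 × share × gap/365.25.

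| Assumed share | Gap | Patient-years | Of placebo/250 miri | Of all miri |
|---|---|---|---|---|
| 1% | 18 days | 0.055 | 0.07% | 0.006% |
| 5% | 28 days | 0.425 | 0.55% | 0.044% |
| 10% | 38 days | 1.155 | 1.50% | 0.119% |

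**5. What the rules do with events and values in the gap.**

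- *Serious adverse events.* Section 6.14.2.2 counts these during the treatment period and states no treatment-emergence condition. A serious event in the gap can be counted.
- *Categorical laboratory values.* Section 6.14.3 uses the postbaseline maximum or minimum, including unscheduled tests. If a value is high early in the gap and normal at the last test before the first mirikizumab dose, baseline is normal and the postbaseline maximum is high. That reads as treatment-emergent although it was measured before the drug.
- *Hepatic thresholds.* Section 6.14.7.1 counts values at or above multiples of the upper limit during the treatment period, so a gap elevation can qualify.
- *Adverse events ongoing at the first injection.* These are baseline events and are not treatment-emergent unless they worsen.
- *Adverse events that start and resolve in the gap.* They are not baseline events and they lie in the postbaseline period, which points to counting them. But a treatment-emergent event is "an event that first occurred or worsened in severity after baseline", and they ended before baseline, which points to not counting them. The two rules give a programmer opposite answers.

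**The case against.** The strongest reply is that little of substance changes, and much of it stands.

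- A reader might infer that every event in the gap becomes a mirikizumab treatment-emergent event. The documents do not support that. Events ongoing at the first injection are baseline events, and for events that start and resolve earlier the definition and the period rule disagree.
- A reader might also extend the point to all placebo patients not dosed at Week 16. Those who never receive mirikizumab are outside the All Active population. Someone whose gap event ended treatment before any mirikizumab is therefore not counted.
- Placebo/250 miri and all miri are in no All Active inferential comparison (Table AMAJ.6.2). The All Active laboratory box plots leave placebo/250 miri out (Table AMAJ.6.8, footnote a).
- Adverse event tables report numbers and percentages of patients. The SAP specifies no exposure-adjusted adverse event rates, so the extra days change no adverse event denominator. The exposure tables carry no p-values.
- Moving the start date alone would do harm. Induction ends before Maintenance starts, so gap events would fall in neither the Induction Safety nor the All Active summary.

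These points limit the size of the problem and shape the repair. They do not remove the mismatch between period start and baseline, or the routes by which serious events and categorical laboratory or hepatic values from the gap can be counted.

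**Conclusion.** The inconsistency holds for placebo patients who are not dosed at Week 16 and receive mirikizumab later. About 18 to 38 days per patient first dosed at Week 20 are counted as mirikizumab exposure before any mirikizumab is given. Serious events and categorical laboratory or hepatic values from those days can be reported under mirikizumab. The status of adverse events that start and resolve in the gap is ambiguous rather than settled against the plan.

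The effect is small and descriptive: at most about 1.5% of placebo/250 miri and 0.12% of all-miri patient-years under the assumptions above (1% to 10% of 111 affected, first dose at Week 20, all completing Week 52). No efficacy result and no planned All Active comparison depends on it. It is still worth correcting, because a stated rule contradicts the baseline in the same SAP and the repair is cheap.

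**What to change.** 1. In Table AMAJ.6.3, start the All Active Treatment Period for placebo/250 miri at the date and time of the first mirikizumab injection. The postbaseline windows in 6.14.2 and 6.14.3 then agree with the baseline already defined there.
2. In 6.14.1, start the exposure interval of these patients at the same point and restrict it to those who received mirikizumab.
3. State where the gap is reported. For safety only, either assign the time from the Week 16 visit or Day 118 up to the first mirikizumab injection to the placebo (Induction) safety period, or list its events separately.
4. Leave the Maintenance Period used for efficacy unchanged.

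The cost is a line in Table AMAJ.6.3, a line in 6.14.1 and a sentence on the gap, and no unblinded data are needed. The downside is a slightly longer placebo safety window for a few patients, or one extra listing.

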6.1.1.2. Definition of Study Baseline

For efficacy and health outcomes, study baseline is defined as the last nonmissing assessment (including unscheduled visits) before the first injection, which in most cases will be the measurement recorded at Week 0 (Visit 2). For efficacy/health outcome measures, if the patient does not take any injection, the last available value on or prior to randomization date will be used. In cases where baseline measurements are taken on the same day as injection, these measurements will be used as the baseline values for data analysis.

For the Psoriasis Symptoms Scale (PSS), the weekly average of at least 4 days of the consecutive 7 days prior to the first injection (or randomization, if the patient does not take any injection) will be the study baseline score.

Baseline for safety analysis is described in the safety section.

6.1.2. Analysis Methods

For assessments of the primary endpoints and other binary efficacy and health outcomes endpoints, the following will be provided:

- Crude proportions for each treatment group along with the 95% two-sided asymptotic (that is, not continuity corrected) confidence intervals (CIs) will be provided.
- The estimated common risk difference along with 95% CIs. The common risk difference is the difference in proportions adjusted for the stratification factors as mentioned in Section 6.2. SAS[®] PROC FREQ will be used for the estimates and CIs, where the CIs are calculated by using Mantel-Haenszel-Sato method (Sato 1989).
- Cochran-Mantel-Haenszel (CMH) test will be used to compare the treatment groups while adjusting for the stratification factors as mentioned in Section 6.2. The CMH p-value will be reported, and the CMH adjusted odds ratio along with the 95% two-sided asymptotic (that is, not continuity corrected) CIs.

When specified as a sensitivity analysis for binary endpoints, logistic regression with a Firth penalized likelihood will be used. The model will include the treatment groups and the covariates described in Section 6.2. Firth correction is equivalent to specifying Jeffrey's prior and seeking the mode of the posterior distribution. Roughly, it adds half of an observation to the data set assuming that the true values of the regression parameters are equal to 0. The likelihood function is adjusted by a fixed quantity, which reduces the positive bias of small samples. The fixed quantity is a function of the information, which goes to 0 as sample size increases. Firth correction can be implemented in PROC Logistic by including *'firth'* as an option in the model statement. The odds ratio and the corresponding 95% CIs, as well as the treatment differences and the corresponding 95% CIs, will be reported.

In addition, when specified as a secondary analysis, pseudo-likelihood-based MMRM (Categorical MMRM, Agresti 2003) estimating the percentage of patients achieving response across postbaseline visits may be used. When MMRM is used, the model includes treatment, baseline value (continuous), visit, the interaction of the baseline value by visit, the interaction of treatment by visit, and the induction/maintenance covariates mentioned in Section 6.2 as fixed factors. The binomial distribution and the logit link function will be used. The residual pseudolikelihood with a subject-specific expansion (RSPL) will be used, which is equivalent to the restricted maximum likelihood (REML). An unstructured covariance matrix will be used to model the within-patient variance-covariance errors. If the unstructured covariance matrix results in a lack of convergence, the heterogeneous Toeplitz covariance structure, followed by the heterogeneous autoregressive covariance structure will be used. The Kenward-Roger approximation will be used to estimate the denominator degrees of freedom. The Newton-Raphson with ridging optimization technique will be used to aid with convergence. The

probability of response, the corresponding 2-sided 95% CI, and the p-value for the treatment comparisons at postbaseline visits will be reported.

Treatment comparisons of continuous efficacy and health outcome variables with multiple postbaseline measurements will be made using MMRM. When MMRM is used, the model includes treatment, baseline value, visit, the interaction of the baseline value-by-visit, the interaction of treatment-by-visit, and the induction/maintenance covariates mentioned in Section 6.2 as fixed factors. The covariance structure to model the within-patient errors will be unstructured. If the unstructured covariance matrix results in a lack of convergence, the heterogeneous Toeplitz covariance structure, followed by the heterogeneous autoregressive covariance structure will be used. The REML will be used. The Kenward-Roger method will be used to estimate the denominator degrees of freedom. Type III tests for the least squares (LS) means will be used for the statistical comparison; the 95% CI will also be reported.

Treatment comparisons of continuous efficacy and health outcome variables with a single postbaseline time point will be made using analysis of covariance (ANCOVA) with the following in the model: treatment group, baseline value, and Induction Period/Maintenance Period covariates mentioned in Section 6.2. Type III tests for LS means will be used for statistical comparison between treatment groups. The LS mean difference, standard error, p-value, and 95% CI, unless otherwise specified, will also be reported. ANCOVA may also be used as a secondary analysis for the MMRM approach, by repeating analysis for each time point.

The Kaplan-Meier (KM) product limit method will be used to estimate the survival for several time to event analyses. The hazard ratio and log-rank test stratified by covariates mentioned in Section 6.2 will be reported. Time for all analyses will be described in units of weeks.

For variables that are not collected at each postbaseline visit, data may exist at visits where the variable was not scheduled to be collected. In these situations, data from the early discontinuation visit that do not correspond to the planned collection schedule will be excluded from the MMRM analysis (Andersen and Millen 2013). Also for by-visit summaries/displays such as boxplots, the weeks when data was not scheduled to be collected may not be displayed. However, unscheduled assessments within any defined study period will still be used in the shift analyses, and for imputing values for the change from baseline to modified baseline observation carried forward (mBOCF) endpoint analyses.

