5.2. Determination of Sample Size

This section is based on the original AMAJ Protocol. The section was not changed in Protocol Amendment (b) due to the completion of the enrollment at the time of Amendment (b) approval.

Approximately 1443 patients will be randomized at a 4:4:4:1 ratio in the Blinded Induction Period to receive 250-mg mirikizumab SC at Weeks 0, 4, 8, and 12, then 250-mg mirikizumab SC Q8W, 250-mg mirikizumab SC at Weeks 0, 4, 8, and 12, then 125-mg mirikizumab SC Q8W, 300-mg secukinumab at Weeks 0, 1, 2, 3, and 4, followed by 300-mg secukinumab Q4W, or placebo. Stratified block randomization will be performed with the following stratification factors: previous exposure to biologic therapy (yes/no), body weight (<100 kg or \geq 100 kg), and geographic region (North America, Europe, or Other).

There are multiple primary endpoints in this study: the proportion of patients achieving a \geq 90% improvement in PASI from baseline (PASI 90) and the proportion of patients with a sPGA (0,1) with at least a 2-point improvement from baseline, comparisons between mirikizumab and placebo (test of superiority), and comparison between mirikizumab and secukinumab (test of non-inferiority). The assumed PASI 90 responses are 70% for the mirikizumab arm, 70% for the secukinumab arm, and 3% for the placebo arm. The assumed sPGA 0 or 1 responses are 70% for the mirikizumab arm, 70% for the secukinumab arm, and 5% for the placebo arm. Both PASI 90 and sPGA (0,1) rates at Week 52 are estimated to be 75% for both mirikizumab dose groups, and 65% for secukinumab group. The assumptions for mirikizumab are based upon the results of the mirikizumab Phase 2 Study I6T-MC-AMAF (Reich et al. 2017b) and review of historical clinical studies in psoriasis (Langley et al. 2014; Gordon et al. 2016; Blauvelt et al. 2017; Papp et al. 2017; Reich et al. 2017a). The assumptions for secukinumab were based upon 2 Phase 3 studies of secukinumab for psoriasis (Langley et al. 2014).

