With 888 patients in the mirikizumab group and 111 patients in the placebo group, the estimated power is at least 99% to test superiority of mirikizumab to placebo on PASI 90 at Week 16, and on sPGA (0,1) at Week 16, respectively, at alpha of 0.05 two-sided. With 888 patients in the mirikizumab group and 444 patients in the secukinumab group, the estimated power is at least 90% to test noninferiority of mirikizumab to secukinumab at alpha of 0.025 one-sided with a noninferiority (NI) margin of 10% on PASI 90 at Week 16. Similarly, the estimated power is at least 90% to test noninferiority of mirikizumab to secukinumab at alpha of 0.025 one-sided with a NI margin of 10% on sPGA (0,1) at Week 16.

In addition, with 444 patients in the 250-mg mirikizumab Q8W group, 444 patients in 125-mg mirikizumab Q8W group, and 444 patients in the secukinumab group, the study will have an estimated power of 90% to test superiority of 250-mg mirikizumab Q8W compared to secukinumab at alpha of 0.05 two-sided on PASI 90 at Week 52, and sPGA (0,1) at Week 52, respectively, as well as 90% power to test superiority of 125-mg mirikizumab Q8W compared to secukinumab at alpha of 0.05 two-sided on PASI 90 at Week 52, and sPGA (0,1) at Week 52, respectively.

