6.6. Active-Control Studies Intended to Show Non-inferiority

There is no universally accepted value for what is considered to be a clinically unimportant difference between 2 treatments in sPGA (0,1) or PASI 90 response. Food and Drug Administration (FDA) guidance (2016) states that an appropriate non-inferiority margin should be based on both clinical and statistical grounds.

For active control treatment secukinumab, the treatment difference between secukinumab 300-mg Q4W dosing and placebo on PASI 90 responses at Week 16 in the pivotal Phase 3 studies were around 71.5% and 70% in the FIXTURE and ERASURE studies, respectively (Langley et al. 2014). In these study designs, there were no placebo controls beyond Week 12. As the PASI 90 rates in placebo patients were very low and few fluctuations were observed in the induction phases of these studies, the PASI 90 rates at Week 12 (1.5% and 1.2% in the FIXTURE and ERASURE studies, respectively) were extrapolated to Week 16 to provide estimates of treatment effect with comparisons to placebo at Week 16. The estimated treatment differences for secukinumab 300 mg Q4W (with placebo) were approximately 70% and 69% in the FIXTURE and ERASURE studies. Due to the consistency of treatment effects in pivotal studies of secukinumab, a fixed NI margin is proposed for Study AMAJ, instead of being based on the synthesis method.

The NI margin of 10% on PASI 90 response is considered to be sufficiently small to be a clinically unimportant difference in outcomes between mirikizumab and secukinumab. It represents clinical judgement about the amount of the active control effect that must be retained. Assuming the observed treatment effects for secukinumab and placebo in Study AMAJ is similar to what have been observed in historical studies, for example, 70%, the proposed NI margin of 10% is expected to preserve a substantial fraction (85.7%) of the secukinumab effect.

Similarly, a 10% NI margin will be used for the other primary endpoint sPGA (0,1) and other secondary endpoints with non-inferiority tests comparing mirikizumab and secukinumab. For more details, please refer to Section 10.3.3 in protocol.

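### The planned asymptotic 95% intervals for each arm's crude response proportion fall short of 95% coverage in the placebo arm: 84.3% at the planned PASI 90 rate of 3% and 91.0% at the planned sPGA (0,1) rate of 5%

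*SAP*

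**What the plan says.** SAP 6.1.2 opens its list of binary outputs with "For assessments of the primary endpoints and other binary efficacy and health outcomes endpoints, the following will be provided". The first output is the crude proportion in each treatment group, "along with the 95% two-sided asymptotic (that is, not continuity corrected) confidence intervals". No score, exact or other small-count alternative is given for these per-arm intervals.

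The other outputs in the same list are separate: a common risk difference with a Mantel-Haenszel-Sato interval, and a stratified CMH test with an adjusted odds ratio. Firth logistic regression is added as a sensitivity analysis.

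SAP 5.2 fixes the setting. "Approximately 1443 patients will be randomized at a 4:4:4:1 ratio in the Blinded Induction Period", and the placebo comparison is planned "With 888 patients in the mirikizumab group and 111 patients in the placebo group". Assumed PASI 90 response is 70% on mirikizumab, "70% for the secukinumab arm, and 3% for the placebo arm". Assumed sPGA (0,1) response is 70% on mirikizumab, "70% for the secukinumab arm, and 5% for the placebo arm". SAP 6.6 also cites placebo results from two earlier Phase 3 trials of secukinumab: "the PASI 90 rates at Week 12 (1.5% and 1.2% in the FIXTURE and ERASURE studies, respectively". Under SAP 6.3.1 missing responses count as nonresponse, so the full-ITT denominator stays at all randomized patients.

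**The concern.** An uncorrected asymptotic interval puts a symmetric normal band around the observed proportion, with a standard error estimated from that same proportion. With a handful of responders the standard error is too small exactly when the estimate is too low. The upper limit then misses the true rate too often. With very few responders the lower limit drops below zero, and with none the interval collapses to a point.

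The placebo arm sits in that range for both primary endpoints. At stake is the accuracy of a reported quantity: tables and figures would label placebo intervals as 95% when they are not, and would understate how high placebo response could be.

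**Working it through.** **Inputs.** n = 111 placebo; p = 3% (PASI 90) and 5% (sPGA 0,1), from SAP 5.2; p = 1.5% and 1.2%, from SAP 6.6; z = 1.96. Reading the interval as Wald is an inference from the contrast with a continuity-corrected form.

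**The plan's own figures first.** 1443 × 1/13 = 111 and 1443 × 8/13 = 888, as stated. For superiority over placebo on PASI 90 the difference is 0.67, with SE = √(0.70×0.30/888 + 0.03×0.97/111) = 0.0223, about 30 standard errors. For sPGA (0,1) it is 0.65 with SE = √(0.70×0.30/888 + 0.05×0.95/111) = 0.0258, about 25 standard errors. The stated power of at least 99% is reproduced.

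**Wald interval for x responders.** x/n ± 1.96 √[(x/n)(1 − x/n)/n], n = 111:

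| x | Wald 95% | P(x) at 3% |
|---|---|---|
| 0 | 0 to 0 | 3.4% |
| 1 | −0.9% to 2.7% | 11.7% |
| 2 | −0.7% to 4.3% | 19.9% |
| 3 | −0.3% to 5.7% | 22.3% |
| 4 | 0.1% to 7.1% | 18.6% |

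**Exact coverage.** Sum the Binomial(111, p) probabilities over every x whose interval contains p.

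- At 3% the interval contains the truth for x = 2 to 8. It misses low for x = 0 or 1 (3.4% + 11.7% = 15.1%) and high for x ≥ 9 (0.6%). Coverage = 100 − 15.1 − 0.6 = 84.3%.
- At 5% it contains the truth for x = 3 to 11. The misses are 8.0% and 1.0%. Coverage = 91.0%.

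| True placebo rate | Wald | Wilson | Clopper-Pearson | P(x = 0) | P(x = 1–3), negative lower limit |
|---|---|---|---|---|---|
| 1.2% | 73.8% | 95.5% | 98.9% | 26.2% | 69.3% |
| 1.5% | 81.2% | 97.4% | 99.3% | 18.7% | 72.7% |
| 2.5% | 93.8% | 93.9% | 97.8% | 6.0% | 63.8% |
| 3% | 84.3% | 95.0% | 98.1% | 3.4% | 53.9% |
| 4% | 93.4% | 95.5% | 97.6% | 1.1% | 33.7% |
| 5% | 91.0% | 95.4% | 95.4% | 0.3% | 18.6% |
| 6% | 89.9% | 95.7% | 97.6% | 0.1% | 9.3% |

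**Sensitivity.** Coverage oscillates with n and p. At p = 3% it is 82.2% for n = 105 and 86.0% for n = 115; at p = 5% it is 89.5% and 92.6%. Over rates from 0.5% to 6% at n = 111, the best of the round values checked is 93.8%, at 2.5%. The same sum in steps of 0.01 percentage points peaks at 94.6%, near 2.65%. It never reaches 95%.

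**Active arms.** Wald coverage is 94.8% (n = 888, 70%) and 94.4% (n = 444, 70%).

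**What the alternative shows.** For 3 of 111, Wilson gives 0.9% to 7.6%. For 0 of 111 it gives 0 to 3.3%.

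**The case against.** The strongest reply is that nothing is decided on this interval. Treatment effects are tested by CMH. The risk difference has its own Mantel-Haenszel-Sato interval, the multiplicity procedure in SAP 6.5 works on adjusted p-values, and noninferiority in SAP 6.6 rests on the mirikizumab-minus-secukinumab difference. All of this stands. A reader might infer that primary inference is at risk because the interval is listed for the primary endpoints; the documents do not support that. Nor would the clinical message change: with 3 of 111 responders, either interval puts placebo in single digits against a planned 70%.

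Second, Wald is not named, and an uncorrected score interval is also asymptotic. This stands as a caveat. If a score interval is meant, coverage is satisfactory and the text needs only to say so.

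Third, 84.3% is one point on an oscillating curve, belonging to one endpoint. This also stands: the other primary endpoint is at 91.0%, and nearby rates reach 93% to 94%. The 1.2% and 1.5% rates are Week 12 results from other trials, not this plan's assumption. But no rate checked reaches 95%, so the direction does not depend on the point chosen.

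Fourth, the Firth sensitivity model is a small-sample safeguard, but for the comparison between arms. It does not repair the per-arm interval. Displaying a negative limit as 0 likewise leaves both coverage and the zero-width interval unchanged.

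**Conclusion.** The point holds as a reporting error confined to sparse placebo responses. Under the Wald reading and the plan's own n and rates, the placebo intervals labelled 95% cover 84.3% (PASI 90) and 91.0% (sPGA 0,1) of the time. At 3% almost all of the shortfall comes from upper limits that are too low. The chance of a negative or zero-width interval there is 53.9% + 3.4% = 57.3%. The consequence is limited to descriptive output; tests, effect estimates, power and sample size stand.

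The method applies to every binary endpoint, but the defect does not: the active arms are near nominal at their planned rates, and placebo patients switch to mirikizumab at Week 16. A reader might also infer that zero placebo responders is likely for PASI 100. The documents give no placebo PASI 100 rate. If it were 1% (an assumption), the chance of none would be 0.99^111 = 32.8%; it passes one half only below about 0.62%. No claim is made for that endpoint.

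**What to change.** In SAP 6.1.2, for the per-arm crude proportions only, replace the asymptotic, uncorrected interval with the Wilson score interval, named as such. Its coverage is 95.0% at 3% and 95.4% at 5%. It also oscillates (93.9% at 2.5%), but it stays close to nominal and gives neither negative limits nor zero width. Clopper-Pearson is an alternative if guaranteed coverage is preferred; it is somewhat conservative (98.1% at 3%, 95.4% at 5%).

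The cost is one SAP phrase and one PROC FREQ option. Placebo upper limits become somewhat higher, for example 7.6% instead of 5.7% with 3 of 111 responders. Testing, alpha allocation and sample size do not change.
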